1.2 Schedule of Activities (SOA)

Table 3: SOA for EUA-dosed Cohort 1

Study Day	D-28 to D-1	1	8 ^b	15	29	91	181	273	366	Illness/ Unscheduled Visit	Early Termination Visit
Visit Number	00 ^a	1	2	3	4	5	6	7	8		
Window (+/-)		0	1	2	2	7	14	28	28		
Informed Consent ^a	X										
Eligibility Criteria	X	X									
Medical History	X	X									
Vaccination ^c		X									
Concomitant Meds		X	X	X	X						
Interim History		X	X	X	X	X	X	X	X	X	X
Physical Exam - Targeted	X	X		X	X	X	X	X	X	X	X
Vital Signs ^d	X	X		X	X					X	X
Height/Weight (BMI) ^a	X										
Urine β-HCG ^e		X									
Memory Aid, Solicited AEs		X	X	X ^f							
Unsolicited AEs		X	X	X	X						
SAEs, Protocol specified AESIs, MAAEs, and NOCMCs			X	X	X	X	X	X	X	X	X
Nasal or NP swab for PCR & Sequencing										X ^g	
Immunoassays											
Serum- Humoral Assays		32		32	32	32	32	32	32		32
PBMC Cellular Assays & plasma		64		64			64		64		64
Daily Volume (mL)		96		96	32	32	96	32	96		96
Cumulative Volume (mL)		96		192	224	256	352	384	480		

^a Optional screening visit – informed consent and height/weight only performed at screening or Day 1

^b Telephone visit

^c Delayed booster dose based upon assignment to Groups 1E-3E (and/or future groups added as adaptive design)

^d Vital signs before and after booster vaccination. Otherwise, only as clinically indicated

^e For women of childbearing potential, a negative urine pregnancy on Day 1 will be performed with negative results confirmed before dosing

^f Review 7-day Memory Aid data.

^g Collect nasal or NP swab for PCR (x2). Sequencing will be performed on all Illness visit-confirmed SARS-CoV-2 specimens.

Table 4: SOA for Prospective Cohort 2 (prior to 2nd booster dose):

Study Day	D-28 to D-1	1	8 ^b	29	36 ^b	43	Delayed Boost to occur ≥ 181 days (window +/- 30 days) from Dose 2	1B	8B ^b	15B	29B	91B	181B	366B	Illness/Unsch Visit	Early Term Visit
Visit Number	00 ^a	1	2	3	4	5		6	7	8	9	10	11	12		
Window (+/-)		0	1	2	3	3		0 ^d	1	2	2	7	14	28		
Informed Consent ^a	X															
Eligibility Criteria	X	X		X				X								
Medical History	X															
Vaccination		X ^c		X ^c				X ^d								
Concomitant Meds	X	X	X	X	X	X		X	X	X	X					
Interim History		X	X	X	X	X		X	X	X	X	X	X	X	X	X
Physical Exam - Targeted	X	X		X		X		X			X	X	X	X	X	X
Vital Signs ^e	X	X		X				X			X	X			X	
Height/Weight (BMI) ^a	X															
Urine β-HCG ^f		X		X				X								
Memory Aid, Solicited AEs		X	X	X	X			X	X	X ^g						
Unsolicited AEs		X	X	X	X	X		X	X	X	X					

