SAEs, Protocol specified AESIs, MAAEs, and NOCMCs			X	X	X	X		X	X	X	X	X	X	X	X	X
Nasal or NP swab for PCR & Sequencing															X ^h	
Immunoassays																
Serum- Humoral Assays		32		32		32		32		32	32	32	32	32		32
PBMC Cellular Assays & plasma		64*		64*		64*	64		64	64	64	64	64		64	
Daily Volume (mL)		96		96		96	96		96	32	96	96	96		96	
Cumulative Volume (mL)		96		192		192	384		480	512	608	704	800			

^a Optional screening visit – informed consent and height/weight only performed at screening or Day 1

^b Telephone visit

^c EUA-dosing with 28-day interval – new constructs may be added as EUA is awarded and vaccine available

^d Delayed booster dose will be the 50 mcg dose of Moderna mRNA-1273. It will be administered on study day 1B which is 181 days with a window of +28 days after the second vaccine dose. If no booster administered; safety visits will continue as per [Table 6](#). If Covid-19 infection is detected in the interval between the primary series and the estimated time of booster administration, volunteers may remain in the study (with a minimum 28 day interval between infection and boost)

^e Vital signs before and after vaccination. Otherwise, only as clinically indicated.

^f For women of childbearing potential, a negative urine pregnancy test on Days 1 and 1B (delayed boost) will be performed with negative results confirmed prior to each dosing

^g Review 7-day Memory Aid data for delayed booster dose.

^h Collect nasal or NP swabs (x 2) for PCR. Sequencing will be performed on all illness visit-confirmed SARS-CoV-2 specimens.

*Collection of PBMC for cellular assays is performed at the discretion of the site, based on the capacity for PBMC processing

Table 5: SOA for Prospective Cohort 2 (2nd booster dose)

Study Day		1C	8C ^b	15C	29C	91C	181C	Illness/Unsch Visit	Early Term Visit
Visit Number		13	14	15	16	17	18		
Window (+/-)		0	1	2	2	7	14		
Informed Consent		X							
Eligibility Criteria		X							
Vaccination		X ^a							
Concomitant Meds		X	X	X	X				
Interim History		X	X	X	X	X	X	X	X
Physical Exam - Targeted		X		X	X	X	X	X	X
Vital Signs ^c		X		X	X			X	
Saliva Mucosal Sample		X		X	X	X	X		X
Nasal Mucosal Sample		X		X	X	X	X		X
Urine β-HCG ^d		X							
Memory Aid, Solicited AEs	Boost to occur ≥ 120 days and ≤ 366 days from Dose 3	X	X	X ^e					
Unsolicited AEs		X	X	X	X				
SAEs, Protocol specified AESIs, MAAEs, and NOCMCs		X	X	X	X	X	X	X	X
Nasal or NP swab for PCR & Sequencing								X ^f	
Immunoassays									

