3 OBJECTIVES AND ENDPOINTS

Table 7: Objectives and Endpoints (Outcome Measures)

OBJECTIVES	ENDPOINTS (OUTCOME MEASURES)
Primary	

 To evaluate the safety and reactogenicity of delayed heterologous or homologous vaccine doses after EUA dosed vaccines. 	
 Local and systemic solicited adverse events for 7 days following the delayed boost dose. Adverse Events from Dose 1 to 28 days following each vaccination and delayed boost dose. MAAEs, SAEs, NOCMCs, and AESIs from Dose 1 to end of planned study participation.

 To evaluate the breadth of the humoral immune responses of heterologous and homologous delayed boost regimens following EUA dosing 	
Response rate, and magnitude of SARS-CoV-2-specific antibody binding and neutralization titers in serum samples as assessed via a range of assays at all timepoints.

Secondary	

 None 	
 None
*Exploratory	

 To assess, in at least a subset of samples, the B cell immune response following EUA vaccination and delayed boost 	
 Magnitude, phenotype and percentage of SARS-CoV-2 specific B cells, as measured by flow cytometry and targeted B cell subset analysis at time points post-vaccination and/or delayed boost.

 To assess, in at least a subset of samples, the SARS-CoV-2 protein-specific T cell responses following EUA vaccination and delayed boost 	
 Magnitude, phenotype, and percentage of cytokine producing S protein T cells as measured by flow cytometry at time points post-vaccination and/or delayed boost.

OBJECTIVES	ENDPOINTS (OUTCOME MEASURES)

 To evaluate breakthrough symptomatic SARS-CoV-2 infection and sequence strains to assess for variant spike lineage 	
 To perform sequence analysis on breakthrough NAAT-confirmed COVID-19 strains to assess for variant spike lineage

 To assess, in at least a subset of samples, mucosal (salivary and nasal) SARS-CoV-2 spike protein-specific IgG and IgA responses 	
 Magnitude and percentage of SARS-CoV-2 spike protein specific IgA and IgG and correlation with serologic antibody response

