infection. They will be assigned to receive COVID-19 vaccine under EUA dosing (as programmatically outlined in Table 9. Additional pools of subjects can be included if needed as additional COVID-19 vaccines are awarded EUA. These pools of participants were to be assigned a novel homologous or heterologous variant boost or heterologous platform boost at a minimum of 12 weeks following receipt of EUA dosing and followed through 12 months after the last vaccination. As booster vaccines have been approved for individuals at an interval of 6 months from the primary series, under EUA, all Cohort 2 volunteers will be offered a booster of mRNA-1273 at the approved 50 mcg dose at Day 181 (+/- 30 days following dose 2 of their primary series. A telephone visit will occur one week after each primary EUA vaccination and one week after the booster dose. In person follow-up visits will occur on 14 days following completion of EUA vaccinations and on days 14, and 28 days after the booster dose, as well as 3, 6, and 12 months post the booster vaccination. A fourth dose of COVID-19 vaccine will be administered to participants using the Moderna mRNA-1273.222 bivalent vaccine at an interval of 4 to 12 months after the third dose (1st booster). In addition to the other immunologic assays planned for earlier parts of the study (including innate, cellular and humoral responses), samples also will be collected to measure mucosal immune responses before the booster dose and on days 14 and 28, and at 3 months and 6 months after the fourth dose (2nd booster). Due to the surge of the Omicron variant and breakthrough infections, volunteers who contract symptomatic or asymptomatic COVID-19 between completion of their EUA primary series and the scheduled booster dose will be allowed to continue in the study. The interval between the COVID-19 infection and booster dosing should be a minimum of 28 days.

Table 9: Cohort 2 Treatment Arms

Group	Sample Size	First Vaccination	Second Vaccination		Booster Vaccination 1		Booster Vaccination 2	
		Product and Dose	Interval	Product and Dose	Interval	Product and Dose	Interval	Product and Dose
1	250	100 mcg mRNA-1273	28 days	100 mcg mRNA-1273	~6 months	50 mcg mRNA-1273	4-12 months	50 mcg mRNA-1273.222

For both Cohorts 1 and 2, reactogenicity will be assessed at the above-mentioned visits and blood will be drawn for immunogenicity assays at the in-person follow-up visits.

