8.3.1.2 Unsolicited Adverse Events

All AEs spontaneously reported by the subject and/or in response to an open question from study staff or revealed by observation, physical examination or other diagnostic procedures must be recorded on the appropriate DCF.

Unsolicited AEs of all severities will be reported from the time of study product administration through 28 days post each vaccination.

After 28 days post last vaccination through the end of planned study participation, only SAEs, AESIs, MAAEs, and NOCMCs (as detailed in [Section 8.3.9](#)) will be reported as AEs.

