8.3.5 Time Period and Frequency for Event Assessment and Follow-Up

For this study:

- solicited AEs will be collected for 7 days post each vaccination.
- unsolicited AEs will be collected until 28 days after each vaccination.
- SAEs, AESIs, MAAEs, and NOCMCs will be collected from Dose 1 to end of planned study participation.

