9.4.4 Safety Analyses

Summaries and analysis of safety data will be presented for the Safety Analysis Population.

Solicited AEs will be summarized by severity for each day post vaccination (Days 1-8) and as the maximum severity over all 8 days. Additionally, solicited AEs will be analyzed using standard techniques, such as exact confidence intervals (CI), to summarize the proportion of subjects reporting each symptom, any application site symptom, and any systemic symptom.

Unsolicited non-serious AEs will be collected from the time of first vaccination through 28 days after the last vaccination. Unsolicited AEs will be coded by MedDRA for preferred term and system organ class (SOC). SAEs, Protocol Specified AESIs, MAAEs, and NOCMCs will be collected from the time of first vaccination to end of planned study participation. The numbers of SAEs, AESIs, NOCMCs and MAAEs will be reported by detailed listings showing the event description, MedDRA preferred term and SOC, relevant dates (vaccinations and AEs), severity, relatedness, and outcome for each event. Non-serious unsolicited AEs will be summarized as number and percentage of subjects reporting at least one event in each MedDRA preferred term and SOC, cross tabulated by severity and relationship to study product. Additionally, the proportion of subjects and exact 95% CIs of AEs in aggregate and by MedDRA categories will be computed.

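### After Cohort 2 Dose 2 the schedule covers only about half of the 28-day unsolicited-AE window, and Section 9.4.4 describes that window as one continuous period

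*Protocol*

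**What the plan says.** Three places in the protocol tie the unsolicited-AE window to each dose. The endpoint in Section 3 (Table 7) is "Adverse Events from Dose 1 to 28 days following each vaccination and delayed boost dose". Section 8.3.1.2 says "Unsolicited AEs of all severities will be reported from the time of study product administration through 28 days post each vaccination". Section 8.3.5 says "unsolicited AEs will be collected until 28 days after each vaccination".

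Section 9.4.4 words it differently: "Unsolicited non-serious AEs will be collected from the time of first vaccination through 28 days after the last vaccination". Sections 8.3.1 and 8.3.1.2 mix the two ideas. Each begins with the per-dose window, but then narrows reporting to SAEs, AESIs, MAAEs and NOCMCs only once 28 days have passed since the last vaccination.

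On contacts in Cohort 2, Table 4 gives the primary series as "EUA-dosing with 28-day interval", so Dose 2 is on Day 29. Section 4.1 adds "A telephone visit will occur one week after each primary EUA vaccination and one week after the booster dose" and "In person follow-up visits will occur on 14 days following completion of EUA vaccinations and on days 14, and 28 days after the booster". The Table 4 header then says "Delayed Boost to occur ≥ 181 days (window +/- 30 days) from Dose 2". Between Day 43 and visit 1B the table has no column.

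**The concern.** Dose 2 is the only vaccination in the trial without a visit 28 days later. Dose 1 has Day 29, the two boosters have 29B and 29C, and Cohort 1 has Day 29. No reason is given for the difference. An event-free Day 44-57 after Dose 2 could mean that nothing happened or that nobody asked until months later. The Dose 2 proportion would then be lower than a fully observed one by an unknown amount, and not comparable with the other doses.

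The wording in Section 9.4.4 adds a second uncertainty. The planned summary is the proportion of subjects with at least one event, so the period chosen decides which subjects enter the numerator. A non-serious event recalled at 1B with onset on, say, Day 120 counts under Section 9.4.4 and does not count under Section 8.3.5.

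**Working it through.** This is calendar arithmetic on the schedule.

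**Inputs.** Dose 2 on Day 29 (Table 4). Last visit 14 days after Dose 2 (Section 4.1), tolerance ±3 days, timed from the actual Dose 2 visit (Tables 4 and 11). Window 28 days (Sections 3, 8.3.1.2, 8.3.5). Visit 1B 181 days after Dose 2, ±30 days in the Table 4 header or +28 days in its footnote d. Second booster at 120 to 366 days after Dose 3 in the Table 5 header, or 120 to 270 days in its footnote a.

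**Check of the plan's own figure.** 29 + 14 = Day 43, as in Table 4.

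**Coverage after Dose 2.**
- Window closes: 29 + 28 = Day 57.
- Not covered by a scheduled contact: 28 − 14 = 14 days, or 50%.
- Visit at +17 days: 28 − 17 = 11 days (39%). Visit at +11 days: 28 − 11 = 17 days (61%).
- Delay from window close to 1B: 181 − 28 = 153 days nominal; 151 − 28 = 123 and 211 − 28 = 183 with ±30 days. Footnote d gives at most 209 − 28 = 181.

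**What could fill the gap.** Visit 1B (nominally Day 29 + 181 = 210) is marked for interim history and unsolicited AEs, so events can be recalled there. The illness/unscheduled and early-termination columns of Table 4 carry no unsolicited-AE mark. Volunteers who do not take the first booster move to Table 6, where the unsolicited-AE row is blank.

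**Length of the two periods.**
- Per dose: 3 × 28 = 84 days through the first booster; 4 × 28 = 112 through the second.
- Section 9.4.4 read literally, with 1B at Day 210: 210 + 28 − 1 = 237 days through the first booster. Through the second: 210 + 120 + 28 − 1 = 357 at the shortest; 210 + 270 + 28 − 1 = 507 under footnote a, or 210 + 366 + 28 − 1 = 603 under the header, at the longest.
- Ratios to 112: 3.2, 4.5 and 5.4.

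**What the schedule would actually collect.** The unsolicited-AE row is blank at 91B, 181B and 366B in Table 4, at 91C and 181C in Table 5, and throughout Table 6. The two wordings can therefore part mainly over events with onset between the close of one window and the next dosing visit, chiefly Day 57 to 1B (210 − 57 = 153 days nominal).

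**The case against.** A reader might infer from Section 9.4.4 that the analysed exposure is 3.2 to 5.4 times the endpoint's window. The documents do not support that as a practical effect. The blank cells listed above show that the trial is run close to the per-dose reading, and the 5.4 depends on one of two conflicting limits in Table 5. Nor is Section 9.4.4 the lone outlier: Sections 8.3.1 and 8.3.1.2 carry similar wording about the last vaccination, and the Table 7 endpoint, which starts at Dose 1, is itself not free of ambiguity. Correcting Section 9.4.4 alone would leave the conflict in place.

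A reader might also infer that the co-primary safety endpoint as a whole is under-ascertained. That goes too far. The gap concerns one component, after one dose, in one cohort. SAEs, AESIs, MAAEs and NOCMCs are collected to the end of participation. Halting rules apply after boosters only. Cohort 2 has a single group and the trial tests no hypothesis, so no between-arm contrast is biased. Dose 2 is part of an authorised primary series, and Section 9.4.6.1 cites the known safety database as the reason for not scheduling SMC reviews in Cohort 2. Onset dates are recorded, so recalled events can be placed in the right interval.

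These limits stand, but they do not close the gap. Table 7 counts AEs after each vaccination, which includes Dose 2. MAAEs are restricted in Section 8.3.9 to events considered related, so a non-serious, medically attended event judged unrelated is outside that safety net unless it also qualifies as an AESI or NOCMC. Recall months later is not equivalent to a 28-day visit, and Table 6 volunteers do not have even that.

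**Conclusion.** The point holds within a narrow scope. For Cohort 2 Dose 2 the protocol states a 28-day unsolicited-AE window of which 14 days (11 to 17) have no scheduled contact. What is known about those days rests on recall 123 to 183 days after the window closes or, for volunteers without a booster, on nothing scheduled. Separately, Sections 8.3.1, 8.3.1.2 and 9.4.4 leave undefined whether events between Day 57 and 1B belong in the analysis.

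This assumes that visits follow the schedule and that boosters fall within ±30 days. Section 7.1.3.1 permits later dosing, which would lengthen recall. How many events would be missed cannot be estimated from the documents. The supplied SAP is unaffected: groups 4E-6E receive one study vaccination, have a Day 29 visit, and Section 9 of that SAP already counts 28 days from the boost. Cohort 2 has its own SAP, which was not available, and it may already settle the wording.

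**What to change.** - **Wording.** Reconcile Sections 8.3.1, 8.3.1.2 and 9.4.4 with Sections 3 and 8.3.5, so that the analysed unsolicited AEs are those with onset within 28 days after each vaccination. Carry the same rule into the Cohort 2 SAP if it is not already there.
- **Reporting.** For Dose 2, show Days 29-43 (collected prospectively) separately from Days 44-57 (recalled), with the number of participants who had any contact covering the second interval. Do not compare the 28-day Dose 2 rate with other doses without that caveat.
- **Collection.** If any Dose 2 administration is still ahead, add one telephone contact at about Day 57. Do not move the Day 36 call to serve this purpose, because under Section 8.2 it is when the 7-day Memory Aid is reviewed.

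The cost is a text amendment, one extra table row and, at most, one call per participant. If Dose 2 dosing is complete, only the first two apply.

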8.3.6 Adverse Event Reporting

8.3.6.1 Investigators Reporting of AEs

Information on all AEs should be recorded on the appropriate DCF. All clearly related signs, symptoms and results of diagnostic procedures performed because of an AE should be grouped together and recorded as a single diagnosis. If the AE is a clinical laboratory abnormality that is part of a clinical condition or syndrome, it should be recorded as the syndrome or diagnosis rather than the individual clinical laboratory abnormality. Each AE will also be described in terms of duration (start and stop date), severity, association with the study product, action(s) taken, and outcome.

8.3.7 Serious Adverse Event Reporting

8.3.7.1 Investigators Reporting of SAEs

Any AE that meets a protocol-defined criterion as an SAE must be submitted immediately (within 24 hours of site awareness) on an SAE form to the DMID Pharmacovigilance Group, at the following address:

DMID Pharmacovigilance Group
Clinical Research Operations and Management Support (CROMS)
[name]
[name]
SAE Hot Line: [name] (US) or [name] (outside US)
SAE [contact] (US) or [name] (outside US)
SAE Email Address: [contact]

In addition to the SAE form, select SAE data fields must also be entered into the SCHARP's EDC system. Refer to the protocol-specific MOP for details regarding this procedure.

Other supporting documentation of the event may be requested by the DMID Pharmacovigilance Group and should be provided as soon as possible. The DMID Medical Monitor will review and assess the SAE for regulatory reporting and potential impact on study subject safety and protocol conduct.

At any time after completion of the study, if the participating site PI or appropriate sub-investigator becomes aware of an SAE that is suspected to be related to study product, the participating site PI or appropriate sub-investigator will report the event to the DMID Pharmacovigilance Group.

8.3.7.2 Regulatory Reporting of SAEs

Following notification from the participating site PI or appropriate sub-investigator, DMID, as the IND sponsor, will report any SUSAR in an IND safety report to the FDA and will notify all participating site PIs (i.e., all PIs to whom the sponsor is providing drug under its IND(s) or under any PI's IND(s)) of potential serious risks from clinical studies or any other source, as soon as possible. DMID will report to the FDA any unexpected fatal or life-threatening suspected adverse reaction as soon as possible, but in no case later than 7 calendar days after the sponsor's initial receipt of the information. If the event is not fatal or life-threatening, the IND

safety report will be submitted within 15 calendar days after the sponsor determines that the information qualifies for reporting as specified in 21 CFR Part 312.32. Relevant follow-up information to an IND safety report will be submitted as soon as the information is available. Upon request from FDA, DMID will submit to the FDA any additional data or information that the agency deems necessary, as soon as possible, but in no case later than 15 calendar days after receiving the request.

SAEs that are not SUSARs will be reported to the FDA at least annually in a summary format which includes all SAEs.

8.3.8 Reporting Events to Subjects

Subjects will be informed of any AEs or SAEs that occur as part of their participation in this trial.

8.3.9 Adverse Events of Special Interest (AESIs)

Adverse Events of Special Interest (AESIs) represent any events for which additional data (besides the standard AE data) are desired. An adverse event of special interest (serious or nonserious) is one of scientific and medical concern specific to the sponsor's product or program, for which ongoing monitoring and rapid communication by the investigator to the sponsor is required. Such an event may require further investigation in order to characterize and understand it. Depending on the nature of the event, rapid communication by the trial sponsor to other parties (e.g., regulators) may also be required. These may be at the request of the regulatory agency, industry partner or DMID, and driven by a regulatory requirement, or known or potential risk from the product or class. Non-structured data similar to SAEs will be collected for AESIs. AESIs encompass the following terms:

Protocol Specified AESIs: See [Section 12](#).

All suspected cases of anaphylaxis should be recorded. For reporting purposes, a participant who displays signs/symptoms consistent with anaphylaxis should be reported as a potential case of anaphylaxis.

Thrombosis with Thrombocytopenia Syndrome (TTS) has been observed very rarely following vaccination with Ad26.COV2.S and is considered an AESI in this study. TTS is a syndrome characterized by a combination of both a thrombotic event and thrombocytopenia. Because this syndrome is rare and not completely understood, all cases of thrombosis and/or thrombocytopenia will be considered a suspected case of TTS until further adjudication can be performed. The investigator shall be responsible for reporting any suspected AESI of TTS using the SAE form. A suspected TTS case is defined as:

- Thrombotic events: suspected deep vessel venous or arterial thrombotic events as detailed in [Section 12](#)
- Thrombocytopenia, defined as platelet count below 150,000/ μ L

Symptoms, signs, or conditions suggestive of a thrombotic event should be recorded and reported as a suspected AESI even if the final or definitive diagnosis has not yet been determined, and alternative diagnoses have not yet been eliminated

or shown to be less likely. Follow-up information and final diagnoses, if applicable, should be submitted to the sponsor as soon as they become available.

In the event of thrombocytopenia, study site personnel should report the absolute value for the platelet count and the reference range for the laboratory test used.

For either a thrombotic event or thrombocytopenia, testing for anti-PF4 should be performed at the local laboratory or substitute local laboratory; repeat testing may be requested for confirmation upon sponsor discretion.

- All suspected cases of myocarditis and pericarditis must be reported as AESI. Symptoms of chest pain, shortness of breath or palpitations may represent myocarditis or pericarditis. Typically, onset of symptoms has been within a few days following receipt of the mRNA COVID-19 vaccines.
- Guillain Barré Syndrome has occurred in some people who have received the Janssen COVID-19 Vaccine and will be recorded as an AESI in this study. In most circumstances, symptoms began within 42 days following receipt of dosing.

NOCMCs – defined as any new ICD diagnosis (per current International Statistical Classification of Diseases and Related Health Problems) that is applied to the subject during the course of the study, after receipt of the study agent, that is expected to continue for at least 3 months and requires continued health care intervention.

MAAEs – defined as a hospitalization, emergency room visit or an otherwise unscheduled visit to or from medical personnel for any reason; and considered related to study product.

All AESIs are assessed, recorded, and followed as described above under AEs. AESIs that meet SAE criteria will be reported on an SAE form within 24 hours to the DMID Pharmacovigilance Group, at the following address:

DMID Pharmacovigilance Group
Clinical Research Operations and Management Support (CROMS)
[name]
[name]
SAE Hot Line: [name] (US) or [name] (outside US)
SAE [contact] (US) or [name] (outside US)
SAE Email Address: [contact]

In addition, for documentation and medical assessment purposes AESIs that do not meet SAE criteria will also be reported on an SAE form and must be submitted immediately (within 24 hours of site awareness) to the DMID Pharmacovigilance Group; however, the narrative will indicate that the AESI did not meet SAE criteria.

